	to 3000 mg/day, however, only a limited number of subjects have received GSK2816126.	clothing with long sleeves, sunglasses, and broad rim hat that protect the skin from sun exposure AND use a broad spectrum sunscreen (e.g., UVA and UVB protective with minimum SPF 30) on any uncovered areas of the body if outdoors from the time of first dose of study medication until at least 2 weeks (14 days) following last dose of study medication due to long elimination phase.
Hepatic Toxicity	
In first in human study EZH117208 (present study), an increase in level of ALT has been noted in the group of subjects receiving doses of 1800 mg to 3000 mg (single infusion dose). None of these ALT increases have been associated with increase in total bilirubin or INR and all have shown improvement following either withholding or discontinuing GSK2816126. The 3000 mg dose has been declared to exceed the MTD. The highest dose being explored in this study is 2400 mg .
 
In nonclinical species given GSK2816126, twice weekly for 2 and/or 4 weeks, changes in liver pathology (inflammation, hyperplasia) in dogs and clinical chemistry parameters (i.e. increases in ALT, AST, alkaline phosphatase (ALP), bilirubin and decreases in albumin) in rats and dogs were observed and were consistent with systemic inflammation. These effects were considered secondary to vascular damage at the infusion and/or surgical site and attributable to vascular or extravascular irritant (vesicant) effects of GSK2816126 and prolonged intravenous catheterization.
 
No current evidence suggests the presence of reactive metabolites. No glutathione conjugates were identified in the in vitro, ex vivo studies that were
	Dosing at 3000 mg has been discontinued, with the highest dose being explored is at 2400 mg. Continued laboratory and clinical monitoring for liver dysfunction (LFT, coagulation parameters INR/PTT, other blood chemistry, clinical observation for jaundice). Dose management and stopping criteria as per guidelines for non-hematologic toxicity (Section 3.8.3 and Table 4) and hepatic safety monitoring (Section 8.3.1)

Potential Risk of Clinical Significance	Data/Rationale for Risk	Mitigation Strategy

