4. For all subjects: Availability of archival tissue, or willingness to undergo fresh biopsy if archival tissue is not available as described in Section 7.6.1.1, Section 7.6.1.2 and Section 7.6.5.
5. Must have a pre-existing central venous access such as a port, Hickmann catheter, or a peripherally inserted central catheter (PICC line) or be willing and able to have one inserted.
6. ECOG Performance Status of 0 or 1 (see [Appendix 2](#)).
7. Men with a female partner of childbearing potential must have either had a prior bilateral vasectomy with resultant azoospermia, bilateral orchiectomy, or must agree to use one of the contraception methods listed in Section 10.1 from the time of the first dose of study medication until at least 2 weeks (14 days) after the last dose of study treatment due to long elimination phase.
8. A female subject is eligible to participate if she is of:
 - Non-childbearing potential as defined in Section 10.1.1
 - Child bearing potential as defined in Section 10.1.1 and agree to use effective contraception, as defined in Section 10.1, for an appropriate period of time (as determined by the product label) prior to the start of dosing to sufficiently minimize the risk of pregnancy and for at least 2 weeks (14 days) following the last dose of study treatment. Women of childbearing potential must have a negative serum pregnancy test within 7 days of first dose of study treatment followed by negative urine or serum pregnancy test once every 4 weeks (prior to next dose cycle) thereafter.
9. Adequate organ system function as defined below:

System	LABORATORY VALUES
Hematologic	
ANC	≥1.2 x 10 ⁹ /L
Hemoglobin	≥9 g/dL
Platelets	≥75x 10 ⁹ /L
PT/INR and PTT	≤1.5 x ULN
Hepatic	
Albumin	≥2.5 g/dL
Total bilirubin	≤1.5 times ULN
AST and ALT	≤2.5 times ULN without liver metastases ≤5 times ULN if documented liver metastases
Renal	
Calculate Creatinine Clearance ^{a, b}	≥50 mL/min
Reproductive/Endocrine for CRPC only	
Testosterone	<50 ng/dL (only for subjects with CRPC)
Cardiac	
Left Ventricular Ejection Fraction (LVEF)	≥LLN (minimum of 50% LVEF) by ECHO or MUGA ^c

Abbreviation(s): ANC, absolute neutrophil count; ALT, alanine aminotransferase; AST, aspartate aminotransferase; ECHO, echocardiogram; INR, international normalization ratio, MUGA, multigated (radionuclide) angiogram; PT, prothrombin time, PTT, partial thromboplastin time, ULN, upper limit of normal, LLN, lower limit of normal.

- a. Calculated by Cockcroft-Gault formula

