ECG ^b	Pre-infusion and at the end of infusion except on Day 1 (Section 7.3.4). Two copies of the ECG tracing should be obtained at the time of the ECG, one to be kept in the study file for retrospective collection by the sponsor if necessary. ECG data should be reviewed by qualified personnel with experience in this study population	X	X ^b	X	X		On Day 4 of each cycle	X

	STUDY PHASE	SCREEN	First Treatment Period Cycle 1			Day 21	Continuation Phase Cycle 2 and beyond	Follow-Up^j
			Day 1 and 4^a	Day 8 and 11^a	Day 15 and 18^a			
	VISIT	Screen						
	VISIT WINDOW (\pmdays)	-14					$\pm 7^l$	$\pm 7^l$
Holter Monitoring	Continuous 12-lead Holter ECGs (obtained via a Holter monitor) will be acquired for a total of approximately 24 hours beginning an hour before infusion on Day 1 only		X (Day 1)					

	STUDY PHASE	SCREEN	First Treatment Period Cycle 1			Day 21	Continuation Phase Cycle 2 and beyond	Follow-Up^j
			Day 1 and 4^a	Day 8 and 11^a	Day 15 and 18^a			
	VISIT	Screen						
	VISIT WINDOW (\pmdays)	-14					$\pm 7^l$	$\pm 7^l$
ECHO /MUGA	At Screening	X						
Concomitant medications	See Section 9.2 for list of prohibited and cautionary medications	X	X	X	X	X	continuous	X
Adverse events (Refer to Section 8)	Adverse event assessment should be continuous	X	X	X	X	X	continuous	X
Blood Sampling: on dosing days, collect blood samples prior to dosing unless otherwise noted								
Chemistry	No need to repeat at pre-dose Day 1 if screening assessments were performed within 72 hours of first dose (- 1 day visit window after screening)	X	X	X	X	X	Prior to every infusion	X

	STUDY PHASE	SCREEN	First Treatment Period Cycle 1			Day 21	Continuation Phase Cycle 2 and beyond	Follow-Up^j
			Day 1 and 4^a	Day 8 and 11^a	Day 15 and 18^a			
	VISIT	Screen						
	VISIT WINDOW (\pmdays)	-14					$\pm 7^l$	$\pm 7^l$
Hematology	No need to repeat at pre-dose Day 1 if screening assessments were performed within 72 hours of first dose (- 1 day visit window after screening)	X	X	X	X	X	Prior to every infusion	X
Coagulation	PT/PTT/INR. No need to repeat at pre-dose Day 1 if screening assessments were performed within 72 hours of first dose (- 1 day visit window after screening)	X						

	STUDY PHASE	SCREEN	First Treatment Period Cycle 1			Day 21	Continuation Phase Cycle 2 and beyond	Follow-Up^j
			Day 1 and 4^a	Day 8 and 11^a	Day 15 and 18^a			
	VISIT	Screen						
	VISIT WINDOW (\pmdays)	-14					$\pm 7^l$	$\pm 7^l$

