15.3. Appendix 3: Liver Chemistry Monitoring, Interruption Stopping and Follow-up Criteria

15.3.1. Liver Safety Stopping Criteria and Required Action and Follow up Assessments

Phase I/II liver chemistry stopping and increased monitoring criteria have been designed to assure subject safety and evaluate liver event etiology (in alignment with the FDA premarketing clinical liver safety guidance).

<http://www.fda.gov/downloads/Drugs/GuidanceComplianceRegulatoryInformation/Guidances/UCM174090.pdf>.

Phase I/II liver chemistry stopping criteria and required follow up assessments

Liver Chemistry Stopping Criteria – Liver Stopping Event Subject with entry criteria $ALT \leq 2.5 \times ULN$	
ALT-absolute	$ALT \geq 5 \times ULN$
ALT Increase	$ALT \geq 3 \times ULN$ persists for ≥ 4 weeks
Bilirubin^{1, 2}	$ALT \geq 3 \times ULN$ and bilirubin $\geq 2 \times ULN$ ($>35\%$ direct bilirubin)
INR²	$ALT \geq 3 \times ULN$ and $INR > 1.5$, if INR measured
Cannot Monitor	$ALT \geq 3 \times ULN$ and cannot be monitored weekly for 4 weeks
Symptomatic³	$ALT \geq 3 \times ULN$ associated with symptoms (new or worsening) believed to be related to liver injury or hypersensitivity
Liver Chemistry Stopping Criteria – Liver Stopping Event Including subjects with documented liver metastases/tumor infiltration at baseline AND entry criteria $ALT > 2.5 \times ULN$ but $\leq 5 \times ULN$	
ALT-absolute	Both $ALT \geq 5 \times ULN$ and $\geq 2 \times$ baseline value
ALT Increase	Both $ALT \geq 3 \times ULN$ and $\geq 1.5 \times$ baseline value that persists for ≥ 4 weeks
Bilirubin^{1, 2}	$ALT \geq 3 \times ULN$ and bilirubin $\geq 2 \times ULN$ ($>35\%$ direct bilirubin)
INR²	$ALT \geq 3 \times ULN$ and $INR > 1.5$, if INR measured
Cannot Monitor	Both $ALT \geq 3 \times ULN$ and $\geq 1.5 \times$ baseline value that cannot be monitored for 4 weeks
Symptomatic³	Both $ALT \geq 3 \times ULN$ and $\geq 1.5 \times$ baseline value associated with symptoms (new or worsening) believed to be related to liver injury or hypersensitivity
Required Actions and Follow up Assessments following ANY Liver Stopping Event	

Actions	Follow Up Assessments

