
Subject with entry criteria ALT≤2.5x ULN ALT ≥3xULN but <5xULN and bilirubin <2xULN, without symptoms believed to be related to liver injury or hypersensitivity and who can be monitored weekly for 4 weeks
 
Subject with documented liver metastases/tumor infiltration at baseline AND entry criteria ALT>2.5 x ULN but ≤5 x ULN ALT ≥3x ULN and 1.5x baseline value but ALT <5x ULN and 2x baseline value and bilirubin <2xULN, without symptoms believed to be related to liver injury, or hypersensitivity and who can be monitored weekly for 4 weeks
	
 • Notify the GSK medical monitor within 24 hours of learning of the abnormality to discuss subject safety. • Subject can continue study treatment • Subject must return weekly for repeat liver chemistries (ALT, AST, alkaline phosphatase, bilirubin) until they resolve, stabilise or return to within baseline¹ • If at any time subject meets the liver chemistry stopping criteria, proceed as described above 
For subjects with entry criteria ALT≤2.5 x ULN
 
 • If, after 4 weeks of monitoring, ALT <3xULN and bilirubin <2xULN, monitor subjects twice monthly until liver chemistries normalize or return to within baseline. 
For subjects with documented liver metastases/tumor infiltration at baseline AND entry criteria ALT>2.5 x ULN but ≤5 x ULN
 
 • If, after 4 weeks of monitoring, ALT <3xULN and <1.5x baseline value, and bilirubin <2xULN, monitor subjects twice monthly until liver chemistries normalize or return to within baseline

1. For the purpose of these guidelines "baseline" refers to laboratory assessments performed closest and prior to first dose of study treatment

References

James LP, , Letzig L, Simpson PM, Capparelli E, Roberts DW, Hinson JA, Davern TJ, Lee WM. Pharmacokinetics of Acetaminophen-Adduct in Adults with Acetaminophen Overdose and Acute Liver Failure. *Drug Metab Dispos* 2009; 37:1779-1784.

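### In subjects entering with liver metastases and ALT above 2.5xULN, the increased-monitoring row and the ALT-only stopping rule do not adjoin, so some ALT rises of 1.5x baseline or more meet neither

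*Protocol*

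**What the plan says.** Protocol Section 5.2.1 admits subjects with AST and ALT up to 5 "times ULN if documented liver metastases". Appendix 3 (Section 15.3.1) gives separate liver rules to those with documented "liver metastases/tumor infiltration at baseline AND entry criteria" ALT above 2.5 and up to 5xULN. For them:

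- **Stopping on ALT alone** requires "Both $ALT \geq 5 \times ULN$ and $\geq 2 \times$ baseline value".
- **Stopping on persistence** requires ALT of at least 3xULN and at least 1.5x "baseline value that persists for" 4 weeks or longer. A further limb uses the same two cut-offs for subjects who cannot be monitored for 4 weeks. Other limbs need raised bilirubin, raised INR or symptoms.
- **Increased monitoring with continued treatment** applies at ALT of at least 3xULN and 1.5x "baseline value but ALT <5x ULN and 2x baseline value and bilirubin" below 2xULN, without symptoms and where weekly monitoring is possible. It brings notification of the medical monitor within 24 hours and mandatory weekly liver chemistries.

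Baseline "refers to laboratory assessments performed closest and prior to first dose of study treatment". The Time and Events Table (Section 7.1) also schedules chemistry at the Cycle 1 dosing visits and Day 21, and from Cycle 2 "Prior to every infusion".

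**The concern.** A monitoring tier and a stopping tier should meet: once ALT passes the trigger, a subject is in one or the other. For subjects entering with ALT up to 2.5xULN they do meet. In the liver-metastases group they do not, because the stopping rule joins its two limits with a both-condition and the monitoring row appears to join its two ceilings in the same way. The complement of a both-condition is an either-condition.

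This concerns the hepatic signal already seen in the trial. Section 1.3.1 reports that "an increase in level of ALT has been noted in the group of subjects receiving doses of 1800 mg to 3000 mg", with 2400 mg still being explored, and it names hepatic safety monitoring under Section 8.3.1 among the mitigations. A subject between the two tiers is not placed on this table's weekly schedule by its wording, although the persistence and cannot-monitor stopping limbs take for granted that such subjects are being followed.

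**Working it through.** **Inputs.** Let b be baseline ALT and a the on-treatment ALT, both in multiples of ULN, with 2.5 < b ≤ 5 (Sections 5.2.1 and 15.3.1). Scope: bilirubin below 2xULN, INR not raised, no symptoms, weekly monitoring possible. That is the situation the monitoring row is written for. The plan states no figure to reproduce.

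**Rules as written.**

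- ALT-only stop: a ≥ 5 and a ≥ 2b. Since b > 2.5, 2b > 5, so the stop begins at 2b.
- Monitoring trigger: a ≥ 3 and a ≥ 1.5b. Since 1.5b > 3.75, the trigger is 1.5b.
- Monitoring ceiling, with "and" meaning both: a < 5 and a < 2b. Since 2b > 5, the ceiling is 5.

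The monitoring band is therefore 1.5b ≤ a < 5. Values at or above the trigger that meet neither rule are max(5, 1.5b) ≤ a < 2b.

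| Baseline b | Trigger 1.5b | Monitoring band | Neither rule | ALT-only stop from 2b |
|---|---|---|---|---|
| 2.75 | 4.125 | 4.125 to <5 | 5 to <5.5 | 5.5 |
| 3 | 4.5 | 4.5 to <5 | 5 to <6 | 6 |
| 3.33 | 5 | empty | 5 to <6.67 | 6.67 |
| 4 | 6 | empty | 6 to <8 | 8 |
| 5 | 7.5 | empty | 7.5 to <10 | 10 |

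**Where monitoring becomes impossible.** The band is empty once 1.5b ≥ 5, that is b ≥ 5/1.5 = 3.33. This covers (5 − 3.33)/(5 − 2.5) = 0.67 of the entry interval. It is a share of a numeric range, not of subjects.

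**Control.** For entry ALT up to 2.5xULN, monitoring is 3 ≤ a < 5 and the stop is a ≥ 5. There is no gap.

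**Alternative reading.** If the ceiling means not (a ≥ 5 and a ≥ 2b), the band becomes 1.5b ≤ a < 2b and the gap closes at every baseline. On that reading the 5xULN term never binds; on the strict reading the 2x-baseline term never binds. Either way one stated limit does no work.

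**What routine chemistry covers.** If the Day 1, 4, 8, 11, 15, 18 pattern continues after Cycle 1, the interval from Day 18 to the next Day 1 (Day 29) is 29 − 18 = 11 days, longer than a week. A held dose has no pre-infusion draw at all.

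**The case against.** The strongest reply is that these subjects are far from unprotected, and most of it stands:

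- Every value in the ranges above becomes a stopping event if it persists for 4 weeks or cannot be monitored, because those limbs have no upper ceiling.
- Section 8.4.2 requires 24-hour reporting of ALT of 5xULN or more, with a liver event form and notification of the sponsor at onset. This largely matches the monitoring row's first action.
- Table 4 (Section 3.8.3) directs a hold for drug-related Grade 3 or 4 non-hematologic toxicity, and Section 1.3.1 cites it for hepatic events.
- Chemistry before each infusion lets persistence be judged in most weeks.

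A reader might infer that the whole range from 5xULN to twice baseline is uncovered, for example 5 to 10xULN at baseline 5. The documents do not support that: the monitoring trigger also requires 1.5x baseline, and at baseline 5xULN the wider range would count an unchanged value as a gap. Values from 5xULN to below 1.5x baseline may be left out deliberately because they lie close to the subject's own entry level.

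Two further points are fair. The compressed wording can be read loosely so that no gap exists, and Figure 2, to which Section 8.3.1 sends readers for this group, is not in the text at hand and might settle the matter. Neither removes the problem. The first half of the same sentence uses the same conjunction to mean both, so sites could defensibly act differently. If the figure differs from the table, the two need aligning anyway.

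**Conclusion.** The point holds in a limited form. On the parallel reading of the monitoring row, isolated asymptomatic ALT rises of at least 1.5x baseline fall under neither that row nor the immediate ALT-only stop: 5 to <6xULN at baseline 3, 6 to <8 at baseline 4, 7.5 to <10 at baseline 5. For baselines of 3.33xULN or more the monitoring row cannot be triggered.

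It would be too strong to say that these values escape the liver rules or go unobserved. The 4-week and cannot-monitor limbs bound the gap, and the other sections act in the meantime. What is lost is the mandatory weekly follow-up, mainly in the off-week and while dosing is held.

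This rests on the strict reading of the ceiling, on baseline lying in the same range as entry ALT, and on Figure 2 not already resolving the wording. The documents do not say how many subjects fall in this group. It should be corrected: the inconsistency bears on a known toxicity and is cheap to remove.

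**What to change.** Reconcile the stopping and increased-monitoring tables in Appendix 3 for the liver-metastases group, and check that Figure 2 agrees, so that at every permitted baseline each ALT value at or above the monitoring trigger falls in exactly one category, monitoring or stopping. State explicitly whether each paired limit means both or either. The sponsor's hepatic safety group should set the thresholds; none is proposed here.

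The cost is amendment wording and possibly an occasional off-week chemistry draw for subjects newly placed under weekly follow-up.

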15.3.2. Liver Safety – Study Treatment Restart or Rechallenge

Guidelines**if subject meets liver chemistry stopping criteria do not restart/rechallenge subject with study treatment unless:**

- GSK Medical Governance approval **is granted** (as described below),
- Ethics and/or IRB approval is obtained, if required, and
- Separate consent for treatment restart/rechallenge is signed by the subject

If GSK Medical Governance approval to restart/rechallenge subject with study treatment **is not granted**, then subject must permanently discontinue study treatment and may continue in the study for protocol-specified follow up assessments

1. **Rechallenge Following Liver Stopping Events that are Possibly Related to Study Treatment**

Following drug-induced liver injury, **drug rechallenge is associated with a 13% mortality across all drugs in prospective studies** [Andrade, 2009]. Clinical outcomes vary by drug, with nearly 50% fatality with halothane readministered within one month of initial injury. However, some drugs seldom result in recurrent liver injury or fatality.

Risk factors for a fatal drug rechallenge outcome include:

- hypersensitivity with initial liver injury (e.g. fever, rash, eosinophilia) [Andrade, 2009]
- jaundice or bilirubin $>2\times$ ULN with initial liver injury (direct bilirubin $>35\%$ of total)
- subject currently exhibits severe liver injury defined by: ALT $\geq 3\times$ ULN, bilirubin $\geq 2\times$ ULN (direct bilirubin $>35\%$ of total), or INR ≥ 1.5
- serious adverse event or fatality has earlier been observed with drug challenges [Papay, 2009]
- evidence of drug-related preclinical liability (e.g. reactive metabolites; mitochondrial impairment [Hunt, 2010])

Rechallenge refers to resuming study treatment following drug induced liver injury (DILI). Because of the risks associated with rechallenge after DILI this should only be considered for a subject for whom there is compelling evidence of benefit from a critical or life-saving medicine, there is no alternative approved medicine available, and a benefit:risk assessment of rechallenge is considered to be favourable.

Approval by GSK for rechallenge with study treatment can be considered where:

- Investigator requests consideration of rechallenge with study treatment for a subject who is receiving compelling benefit with study treatment that exceeds risk, and no effective alternative therapy is available.
- Ethics Committee or Institutional Review Board approval for rechallenge with study treatment must be obtained, as required.
- If the rechallenge is approved by GSK Medical Governance in writing, the subject must be provided with a clear description of the possible benefits and risks of study treatment administration, including the possibility of recurrent, more severe liver injury or death.
- The subject must also provide signed informed consent specifically for the rechallenge with study treatment. Documentation of informed consent must be recorded in the study chart.
- Study treatment must be administered at the dose specified by GSK.
- Subjects approved by GSK Medical Governance for rechallenge with study treatment must return to the clinic twice a week for liver chemistry tests until stable liver chemistries have been demonstrated and then standard laboratory monitoring may resume as per protocol.
- If after study treatment rechallenge, subject meets protocol-defined liver chemistry stopping criteria, study treatment should be permanently discontinued.
- Medical Monitor, and the Ethics Committee or Institutional Review Board as required, must be informed of the subject's outcome following study treatment rechallenge.
- GSK to be notified of any adverse events, as per Section 8 of the protocol.

2. *Restart Following Transient Resolving Liver Stopping Events NOT Related to Study Treatment*

Restart refers to resuming study treatment following liver stopping events in which there is a clear underlying cause (other than DILI) of the liver event (e.g. biliary obstruction, pancreatic events, hypotension, acute viral hepatitis). Furthermore, there should be no evidence of alcoholic hepatitis or hypersensitivity, and the study treatment should not be associated with HLA markers of liver injury.

Approval by GSK for study treatment restart can be considered where:

- Investigator requests consideration for study treatment restart if liver chemistries have a clear underlying cause (e.g., biliary obstruction, hypotension and liver chemistries have improved to normal or are within 1.5 x baseline and ALT <3xULN).
- Restart risk factors (e.g. fever, rash, eosinophilia, or hypersensitivity, alcoholic hepatitis, possible study treatment-induced liver injury or study treatment has an

HLA genetic marker associated with liver injury (e.g. lapatinib, abacavir, amoxicillin/clavulanate) are reviewed and excluded

- Ethics Committee or Institutional Review Board approval of study treatment restart must be obtained, as required.
- If restart of study treatment is approved by GSK Medical Governance in writing, the subject must be provided with a clear description of the possible benefits and risks of study treatment administration, including the possibility of recurrent, more severe liver injury or death.
- The subject must also provide signed informed consent specifically for the study treatment restart. Documentation of informed consent must be recorded in the study chart.
- Study treatment must be administered at the dose specified by GSK.
- Subjects approved by GSK Medical Governance for restarting study treatment must return to the clinic once a week for liver chemistry tests until stable liver chemistries have been demonstrated and then laboratory monitoring may resume as per protocol.
- If after study treatment re-start, subject meets protocol-defined liver chemistry stopping criteria, follow usual stopping criteria instructions.
- Medical Monitor, and the Ethics Committee or Institutional Review Board as required, must be informed of the subject's outcome following study treatment restart.
- GSK, or designee, to be notified of any adverse events, as per Section 8.

References:

Hunt, CM. Mitochondrial and immunoallergic injury increase risk of positive drug rechallenge after drug-induced liver injury: A systematic review. *Hepatol.* 2010;52:2216-2222.

